4.2.3 Data and Safety Monitoring Plan

The Principal Investigator ([name]) and Co-Investigator ([name]) will be responsible for regular monitoring of data and safety in conjunction with an Independent Safety Officer: [name], Chief of the Stanford Prevention Research Center in the Stanford University School of Medicine. [name] is board certified in internal medicine, cardiovascular disease, and clinical lipidology and has extensive expertise in leading clinical trials. He will be responsible for reviewing clinical trial data, with particular emphasis on adverse events or clinical safety. As the Independent Safety Officer, [name] will not be involved in the study's design and conduct nor have any conflict of interests related to the trial. Based on his review of the data, he may propose modifications to the study.

Information that will be monitored by the PI include: (1) adverse events and serious adverse events (SAE) occurring during the study period for events both related and unrelated to the study procedures; (2) feedback from participants about discomfort they are experiencing as a result of completing intervention components; (3) feedback from participants about discomfort related to survey questions or other study procedures; (4) unexpectedly high weight change over time; and (5) any breach of confidentiality.

[name] will provide at least yearly updates to the investigator team regarding recruitment rates, enrollment rates, participant demographics, retention rates, adverse events, and any other substantive trial-related issues. All team members, including investigators, study staff, and students, will be listed on the IRB protocol and will have up-to-date ethics training (CITI certification). All study procedures involving participant contact will be done by trained research staff who have completed formal human subjects training (e.g., CITI Certification) to ensure understanding of methods and procedures to protect personal health information, and the importance of maintaining the confidentiality of study participants. [name] and her study team (Project Coordinator, Research Assistants) will meet weekly during the clinical trial period and will be able meet more frequently if needed.

4.2.4 Adverse Events

Definitions:

- **Serious Adverse Event (SAE):** Any adverse event temporally associated with the subject's participation in research that meets any of the following criteria:
 - Results in death
 - Is life-threatening (places the subject at immediate risk of death from the event as it occurred)
 - Requires inpatient hospitalization or prolongation of existing hospitalization
 - Results in a persistent or significant disability/incapacity
 - Results in a congenital anomaly/birth defect
 - Any other adverse event that, based upon appropriate medical judgment, may jeopardize the subject's health and may require medical or surgical intervention to prevent one of the other outcomes listed in this definition
 - Examples: chest pain; myocardial infarction (heart attack); stroke; kidney stones; knee replacement; car accident resulting in hospitalization; a fall resulting in hospitalization; fracture
- **Unanticipated problem (UP)** involving risks to subjects or others: Any incident, experience, or outcome that meets all the following criteria:
 - Unexpected (in terms of nature, severity, or frequency) given (a) the research procedures that are described in the protocol-related documents, such as the IRB-approved research protocol and informed consent document; and (b) the characteristics of the subject population being studied
 - Related or possibly related to a subject's participation in the research

- Suggests that the research places subjects or others at a greater risk of harm (including physical, psychological, economic, or social harm) related to the research than was previously known or recognized
- a regular Adverse Event (AE): Any untoward or unfavorable medical occurrence in a human subject, including any abnormal sign (for example, abnormal physical exam or laboratory finding), symptom, or disease, temporally associated with the subject's participation in the research, whether or not considered related to the subject's participation in the research
 - Examples: Skin irritation on wrist from wearing accelerometer wristband; migraine; back pain; knee pain; COVID-19 diagnosis; a cold

Information will be collected on all potential types of adverse events, including musculo-skeletal soreness and injury, as well as major medical events including injuries or conditions that result in health care provider visits or hospitalization. Serious adverse events will be reported promptly in writing to the NIH and Stanford IRB, and all adverse events reported to the appropriate entities as required throughout the study.

Participants will be provided with contact information for the study team, including a study phone number and study email address that will be checked daily on business days by study staff and/or the PI. This contact information will be provided to participants on multiple occasions, including in the informed consent form, in weekly intervention-related emails, and in the study assessment emails sent at baseline, 1 month, 3 months, and 6 months. In addition, participants will speak to study staff via phone/video conference at the beginning of the study (before randomization) to ensure eligibility, interest, and understanding of study procedures and assigned intervention components. During this call, participants will be encouraged to report any adverse events, serious adverse events, or discomforts that arise during the trial to the study team.

Study staff will be the primary source of contact with participants (e.g., sending intervention materials and confirming completion of assessments). Study staff will alert the PI of any negative participant feedback. Based on participant feedback, the PI will revise the intervention and study procedures as necessary to ensure that risks of injury or discomfort are minimized and will seek IRB approval before doing so. Study staff will flag any unexpectedly high changes in weight and will notify the PI and Co-Investigator of this occurrence. The Independent Safety Officer will then be asked to review these outcomes and help decide next steps, such as whether a participant will be asked to drop out of the trial for safety reasons. Study staff will present all serious adverse events (SAE) and Unexpected Events to the PI by telephone or electronically within 24 hours of the time they are reported, except for life-threatening events where the expectation is that the PI will be alerted immediately. An internal project-specific report will be

generated in REDCap for each event reported. This information will be provided to the Stanford University IRB and NIDDK in a timely manner, in accordance with a protocol approved by the IRB and NIDDK. The study team will collect several channels of contact information for each participant (with their permission), including phone number(s) and e-mail address(es), along with those of a close friend or family member. In addition to standard study purposes, this contact information will be used to reach participants if additional information about an adverse event or SAE is needed. All study staff will have access to each other's contact information, including an email address and phone number, in a centralized database to facilitate easy communication.

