3.8 Outcomes

All measures collected are listed in **Table 3**, below.

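### Section 4.2.4 promises information on all types of adverse events but describes no scheduled question about them after randomization, so counts are probably incomplete and may not be comparable across conditions

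*Protocol*

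**What the plan says.** Section 4.2.4 sets a wide scope: "Information will be collected on all potential types of adverse events", among them soreness, injury and events leading to a provider visit or hospitalization. Its definition of an adverse event is equally wide. It covers any unfavorable medical occurrence, "whether or not considered related to the subject's participation in the research", and its examples include a cold, migraine, back pain and knee pain.

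The same section then describes how events reach the study team:

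- A study phone number and email address, checked on business days. "This contact information will be provided to participants on multiple occasions": in the consent form, the weekly intervention emails and the assessment emails.
- A call held before randomization: "During this call, participants will be encouraged to report any adverse events, serious adverse events, or discomforts that arise during the trial".
- Staff pass negative participant feedback to the principal investigator.
- Staff flag unexpectedly high changes in weight, which the Independent Safety Officer then reviews.

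A REDCap report is made for each event that is reported. Section 3.8 says of the assessment schedule: "All measures collected are listed in" Table 3. That table has no adverse-event row at 0, 1, 3 or 6 months.

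**The concern.** The stated scope needs a method that asks. The method described mostly waits to be told. A participant in a fully remote program without counseling has little reason to contact the team about a cold or a sore knee, yet both are adverse events under the protocol's definition.

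Two things are at stake. First, under section 4.2.3 the Independent Safety Officer reviews trial data with particular attention to adverse events, and a low count could not be told apart from low reporting. Second, anyone who later tabulates events by condition would be comparing reporting habits as well as event rates.

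**Working it through.** The protocol gives no adverse-event rate or reporting rate, so it has no figure to reproduce. The check is a comparison of the text, followed by an illustration on assumed values.

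**1. Scope against method**

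| Element | Where | Asks the participant after randomization? |
|---|---|---|
| Contact details in emails | 4.2.4 | No; the participant must write or call |
| Encouragement to report | 4.2.4 | No; given once, before randomization |
| Relay of negative feedback | 4.2.4 | No; acts on what is volunteered |
| Flag for high weight change | 4.2.4 | Active, but covers weight only |
| REDCap event report | 4.2.4 | No; starts once an event is reported |
| Surveys at 1, 3 and 6 months | Table 3 | No adverse-event item listed |

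Table 3 is otherwise detailed, down to a one-item confidence measure, so an adverse-event question would be expected to appear there.

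**2. What differs by condition**

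- Participants and staff are unmasked (3.9.1).
- Weekly feedback emails go to conditions 2-8 only (3.5).
- Daily weights, on which the weight flag can act, are asked for only in conditions 2, 4, 6 and 8 (3.2, 3.6).
- The contact details (4.2.4) and the weekly lesson email (3.5) go to everyone.

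**3. Size of under-counting (assumed values)**

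N = 176 (section 2.1), so 176/2 = 88 per level of a component and 176/8 = 22 per condition, if balanced. Expected number with a reported event = 88 × true risk × reporting probability. Take a true risk of 20% in both levels.

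- Full reporting: 88 × 0.20 = 17.6 per level.
- 50% reporting in both: 88 × 0.20 × 0.50 = 8.8 per level. Half are lost, but the ratio stays 1.0.

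**4. Size of bias if reporting differs across a whole component level (assumed values)**

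The apparent risk ratio is the ratio of the reporting probabilities. The last column is the chance of a nominally significant false excess in the better-reporting level (normal approximation, two-sided 5% test). With equal reporting it would be 2.5% in that direction.

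| Reporting | Expected counts | Apparent ratio | False excess |
|---|---|---|---|
| 60% v 50% | 10.6 v 8.8 | 1.2 | 6% |
| 70% v 50% | 12.3 v 8.8 | 1.4 | 13% |
| 80% v 50% | 14.1 v 8.8 | 1.6 | 22% |

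Over the same three rows the chance runs from 5% to 12% at a 10% true risk, and from 9% to 44% at 40%.

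**5. The feedback email taken alone**

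Condition 1 is the only one without feedback emails. It is one of the four conditions in the No level of every component. If it reports at 50% and the other seven at 70%, the No level averages (3 × 70 + 50)/4 = 65%. The main-effect ratio is then 70/65 = 1.08, not 1.4. Ratios of the size in step 4 need a reporting difference across a whole component level, for example from unmasked reporting.

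**The case against.** **The absence is inferred from silence.** The survey forms are not reproduced, and section 4.2.4 never says that spontaneous report is the sole route. Table 3 is also imperfect: it marks diet quality at baseline only, although section 3.8.2 names 6-month change in diet quality as an outcome. It is fair, then, that an unlisted question might exist. But section 3.8 says the list is complete and section 4.2.4 describes no such question, so the protocol as written does not support its own claim. Either way it needs correcting.

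**A reader might infer that events come only from unprompted reports.** That goes too far. Staff actively flag weight change, participants are encouraged to report, and contact details are repeated throughout. What is missing is scheduled, structured questioning.

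**A reader might infer that counts are in fact uneven, with step-tracking participants over-reporting because of extra device contact.** The documents do not support this. In section 3.4.2 the tracker is mailed and synced before the intervention begins, and every participant also receives and syncs an e-scale. Assuming that step conditions report 1.5 times as readily and finding a 50% excess only restates the assumption. Uneven reporting is a risk, not a finding.

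**No aim compares adverse events by condition, and the study is described as minimal risk.** This stands and limits the consequence. It does not remove the gap for safety review or for anyone who tabulates harms by condition.

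**Conclusion.** The point holds in a limited form. The protocol claims to collect information on all types of adverse events, but its described method is participant-initiated reporting plus a weight flag, and its schedule of measures has no adverse-event item. Counts are probably incomplete, most of all for minor events.

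Comparability across conditions is in doubt because of unmasked reporting and unequal email contact. The protocol neither quantifies this nor plans such a comparison. The losses and ratios shown rest on assumed true risks, assumed reporting probabilities and balanced allocation. They show what could happen, not what did. The feedback-email difference alone would shift a main-effect ratio only slightly under those assumptions (1.08).

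This should be corrected. It does not bear on the primary weight outcome.

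**What to change.** **As a design:** put one standard question in the existing 1-, 3- and 6-month surveys, worded identically in all 8 conditions, on any new injury, illness, provider visit or hospitalization since the last assessment. List it in Table 3, and tabulate solicited and spontaneous reports separately. The cost is a small participant burden and staff time to review replies.

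**For this trial:** section 6, Table 4 records that data collection has finished, so the question can no longer be added. Reconcile sections 3.8, Table 3 and 4.2.4 instead.

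- If such a question was asked, add it to Table 3 and section 4.2.4.
- If not, replace the claim to cover all potential types with a statement that events were spontaneously reported, apart from the staff weight flag. State this wherever adverse events are reported, and do not interpret the counts as complete or comparable across conditions.

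This costs a few sentences. The standard question can go into the later evaluation trial foreseen in section 2.6.

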4.2.5 Data Quality

Data quality will be assured by using standardized procedures via comprehensive intervention and assessment protocols. [name] will also closely monitor the data and will use IRB-approved documentation strategies of research procedures. Any updates to the protocol will first receive approval from the IRB before implementing.

4.3 Privacy

Confidentiality of participant data will be maintained by: 1) handling individual data by participant ID number, rather than by name; 2) storing all individual data in password protected files and electronic hard drives, and in encrypted data servers at Stanford; 3) not disclosing individual data to anyone other than trained study staff; 4) using the Stanford protected version of Qualtrics and REDCap, allowing encrypted transmission of all survey data; 5) presenting study findings in aggregate in publications, presentations, and all other dissemination efforts.

Investigators will be sensitive to issues surrounding confidentiality and other forms of participant risk, including discomfort surrounding talking about personal health issues and behaviors. The study team's onboarding meeting will include a discussion of confidentiality and how this is to be maintained throughout the course of the study. All staff will have taken the required online human subjects course on this topic (e.g., CITI training). In addition, this topic will be regularly addressed during weekly staff meetings where staff will be encouraged to ask questions pertaining to this issue.

If data sharing is required, we will transfer data electronically in accordance with the following guidelines: Transmission of data will be done using File Transfer Protocol (FTP) and encrypted through the use of 128-bit SSL or other industry acceptable methods. Wireless communication will be encrypted using Wi-Fi Protected Access (WPA), VPN, or 128-bit SSL.

5 Dissemination

5.1 Data Sharing Plan

The clinical trial is registered at ClinicalTrials.gov (NCT05249465) and information about the results will be submitted there for public posting. Results information will be submitted no later than one year after the trial's primary completion date. Consent documents for this trial will include a specific statement relating to posting of clinical trial information at ClinicalTrials.gov.

The Stanford University School of Medicine has an internal policy in place to ensure that clinical trials registration and results reporting occur in compliance with policy requirements. Specifically, the policy states that the PI will be the Responsible Party for registering, updating, and reporting results from the clinical trial in a timely manner. Registration was completed via the Stanford ClinicalTrials.gov Protocol Registration System (PRS).

Commensurate with current requirements, once the study data have undergone final data cleaning, analysis, and planned publications, we will make the final data collected as part of the proposed research available in electronic form to researchers who request them. We will request that researchers submit a data request in writing to the project Principal Investigator so that the requested data can be made available while protecting the confidentiality of study participants and ensuring that the proposed research questions do not overlap with planned publication development by the project research team or other groups. The requested dataset will be free of identifiers that would permit linkages to individual research participants and we will remove protected health information in compliance with the HIPAA Privacy Rule. The requestor must agree to maintain the privacy and confidentiality of the data and must indicate how they plan to store the data to demonstrate compliance with secure computing. NIH guidelines, institutional policies, IRB rules, and regulatory policies will be taken into account. Per NIH guidelines, all publications that emerge from this award will be publicly available via PubMed Central.

Study results will be shared through presentations at national conferences of professional organizations (e.g., Society of Behavioral Medicine; The Obesity Society), articles in peer-reviewed journals, and postings on social media channels.

5.2 Access to Data

The principal investigator will retain access to the final trial dataset.

6. Protocol Amendment History

The Stanford University Institutional Review Board (IRB) approved our study protocol on March 28, 2022. Additional details were added to the study protocol prior to the trial beginning on September 22, 2023. No substantive changes to the IRB protocol were made once the trial began. Only minor protocol changes were made after this date, including the following, in **Table 4**, below:

Table 4. Protocol Amendments in the Spark Trial.

Version	Approval Date	Description of Change	Brief Rationale
1.0	Mar. 25, 2022	None (original IRB approval)	--
1.1	June 28, 2023	Changed Protocol Director to [name] (from [name]); added new team personnel; added [name] as Independent Safety Officer; changed ASA24 recall reimbursement from \$12 to \$10; modifications to eligibility screen and surveys; added recruitment flyers; updated orientation slides	[name] submitted the IRB application as a postdoctoral fellow but is now an Instructor at Stanford; new study personnel joined the team; identified a Safety Officer without prior PI collaborations; modified incentives for ASA24 due to increased costs of shipping Fitbit devices; updated questions before trial deployment
1.2	Sept. 21, 2023	added new team personnel	New study personnel joined the team.
Trial began on September 22, 2023			
1.3	July 2, 2024	added StudyPages as an online recruitment source; added a new vendor for purchasing Fitbit devices; updated office address on the informed consent form; updated the Google and Fitbit Privacy Policy and Terms of Service documents; added new team personnel	Expand recruitment strategy; discontinuation of original Fitbit vendor; change in office address; change to Google and Fitbit legal documents; new study personnel joined the team.
1.4	Aug. 28, 2024	added new team personnel	New study personnel joined the team.
1.5	Dec. 13, 2024	added new team personnel	New study personnel joined the team.
1.6	June 12, 2025	Stylistic/typographical updates to the protocol and updated recruitment dates and ClinicalTrials.gov status information; added new version of ASA24	Improve readability of the document; provide actual recruitment dates; ASA24 retired version-2022 in April 2025
